**Secondary Efficacy Endpoint / Variables – Descriptive Summary**

- Forced expiratory volume in 1 second (FEV1) at Days 1, 56 and 90.
- Patient Global Impression of Change (PGIC) at Days 14, 28, 56 and 90.
- Patient Global Rating of Severity (PGRS) at Days 1 and 90.
- Sniff nasal inspiratory pressure (SnIP) at Days 1, 56 and 90.
- Physical activity measures as assessed via an accelerometer at Days 1, 56 and 80.

**Summary Results Presentation**

Baseline, each postbaseline visit and change from baseline, will be descriptively summarized by treatment group for endpoints: weekly average steps, vector magnitude unit/wear time and moderate/vigorous activity duration measures via an accelerometer. The number of subjects with the eligible days i.e. wear duration more than 8 hours for at least 4 days, the average eligible days for those subjects and average wear duration (minutes) during the eligible days will be summarized.

Baseline, each postbaseline visit and change from baseline, will be descriptively summarized by treatment group for original FEV1 (L) and percentage predicted FEV1 and maximum SnIP.

In addition, a box plot will be prepared for the change from baseline for FEV1 and SnIP at the post-baseline visits.

For the categorical endpoints, PGRS and PGIC, the count and percentage will be summarized by category and treatment for each visit separately by gender.

**7.3. Exploratory Efficacy Analyses**

**7.3.1. Endpoint / Variables**

The exploratory endpoints that will be analysed are:

- Changes from baseline in handgrip strength.

**7.3.2. Summary Measure**

Descriptive summary of baseline assessments, post-baseline assessments and change from baseline for handgrip strength.

Changes from baseline in size of inspiratory muscles and/or other organs will not be analyzed in this report because there is no data collected. In addition, exit interview data will be reported separately, thus the analysis of the endpoint ‘Gain further insights into the participants’ experience with study treatment and their participation in the trial’ will not be performed in this RAP. The adherence to the exercise program (daily physical activity and thrice-weekly strengthening exercises) will not be explored in this RAP.

**7.3.3. Population of Interest**

The exploratory efficacy analyses will be based on the Analysis population, unless otherwise specified.

**7.3.4. Statistical Analyses / Methods**

Details of the planned displays are provided in [Appendix 11](#): List of Data Displays and will be based on GSK data standards and statistical principles.

Unless otherwise specified, endpoints / variables defined in [Section 7.2.1](#) will be summarised using descriptive statistics, graphically presented (where appropriate) and listed.

**7.3.4.1. Statistical Methodology Specification**

Endpoint / Variables

 
• Changes from baseline in handgrip strength.
 

Summary Results Presentation

 
• The handgrip strength of left hand and right hand will be separately summarized for baseline, Day 90 and change from baseline at Day 90 by treatment for each gender separately
 

### 7.3.4.2. Other Analyses

- An exploratory analysis will be performed on the analysis population to identify how the change from baseline of PROactive total and domain scores changes over the responses of PGIC questionnaire. This relationship between PGIC levels and change from baseline in PROactive total and domains scores will be explored by a descriptive summary table for the visits Day 56 and 90. This comparison will be by gender (males, females and overall (male + female)) and not with respect to treatment. Along with the seven levels of PGIC, the pooled categories “Much worse and Worse” and “Better and Much Better” will also be summarized.
- A sensitivity analysis has to be performed to identify the influence of center PPD on the primary analysis. The primary analysis of percentage change from baseline for leg press has to perform by removing the subjects recruited from the center PPD for the analysis population. This is the analysis supporting the SPOOS ((Significant Payments of Other Sorts) impact analysis.

#### Plots to be generated in R-shiny App

Shiny is an open R package from RStudio, which provides a web application framework to create interactive web applications (visualization) called “Shiny apps”. Shiny combines the computational power of R with the interactivity of the modern web. Shiny web apps can be deployed locally or on the web through tools such as RStudio Connect.

The below mentioned plots will be generated in the R-shiny app at SAC. These displays will then be sent for clinical review. From the generated plots only the clinically important ones will be identified and added to the CSR and will be considered post hoc analyses. These plots will be generated for the analysis population.

- Absolute, Change and percent change from baseline in the leg press strength and change from baseline in constant work rate (CWR) duration from endurance shuttle walking test and peak performance from incremental shuttle walking test versus baseline SPPB categories will be plotted (box-plot) by treatment group for each gender separately. The box-plots for both the treatment groups will be presented in one plot for one gender; then repeat for the other gender.
- The relationship between absolute, change and percent change from baseline at Day 90 in the leg press strength , change from baseline in constant work rate (CWR) duration from endurance shuttle walking test at Day 90 and peak performance from incremental shuttle walking test at Day 90 versus baseline PROactive scores for all the domains score as well as the baseline average daily steps via an accelerometer will be explored by the scattered plots by treatment group for each gender. Baseline scores will be the x-axis and absolute or change from baseline or percent from baseline at Day 90 in the leg press strength and shuttle walk tests separately will be the y-axis
- Mean absolute, change from baseline and percentage change from baseline in leg press strength, change from baseline in appendicular and total lean mass, constant work rate (CWR) duration from endurance shuttle walking test, peak performance from incremental shuttle walking test, total SPPB score, hand grip, SGRQ (all domains) and PROactive (all domains) will be plotted by treatment group for each gender, where descriptive mean for absolute, change from baseline and percentage change from baseline for the respective endpoints will be the Y-axis in each plot and X-axis will be the visits.

## 8. SAFETY ANALYSES

The safety analyses will be based on the safety population and actual treatment group, unless otherwise specified. Data for male and female subjects will be analysed separately.

### 8.1. Adverse Events Analyses

Adverse events analyses including the analysis of adverse events (AEs), Serious (SAEs) and other significant AEs will be based on GSK Core Data Standards. The AE text recorded in the eCRF will be coded using the Medical Dictionary for Regulatory Activities (MedDRA version 22.0) and will be reported using the primary System Organ Class (SOC) and Preferred Term (PT). Results will be displayed irrespective of treatment phase in the order of decreasing frequency, both across SOC and within SOC. The details of the planned displays are provided in [Appendix 11](#): List of Data Displays.

For those displays with maximum intensity, if AEs are reported more than once by a subject, the most severe intensity will be included. An adverse event will be considered as a common adverse event if it occurs in more than one patient in either gender.

### 8.2. Adverse Events of Special Interest Analyses

The table in [Section 12.6.3](#) (“Safety”) presents the Adverse Events of Special Interest (AESI) and the groups of terms that they comprise. AESI which are not standardized MedDRA queries (SMQs) comprise a selection of PTs defined by GSK. The final list of AESIs, and the PTs that contribute to each of the AESIs, will be provided by Safety and Medical Governance (SMG), using the MedDRA version current at the time of reporting. This list will be finalized prior to unblinding the database.

Changes to the MedDRA dictionary may occur between the start of the study and the time of reporting. Furthermore, emerging data from on-going studies may highlight additional AESI. Therefore, the list of AESI, and the terms included for each AESI, will be based on the safety review team (SRT) agreements in place at the time of reporting. The details of the planned displays are provided in [Appendix 11](#): List of Data Displays.

### 8.3. Clinical Laboratory Analyses

Laboratory evaluations including the analyses of Chemistry laboratory tests, Haematology laboratory tests, Urinalysis, Lipids and liver function tests will be based on GSK Core Data Standards. The details of the planned displays are in [Appendix 11](#): List of Data Displays.

A line plot of the mean change from baseline (latest pre-dose value including unscheduled visits) as well as +/- standard error over time (day) for each treatment by gender will be plotted for below mentioned sex hormones and metabolic analytes.

#### Sex / Reproductive Hormones

Testosterone, Free Testosterone, Sex hormone-binding globulin (SHBG), Follicle-stimulating hormone (FSH), Luteinizing hormone (LH) and Prostate specific antigen (PSA).

### Metabolic Analytes

Total Cholesterol, LDL Cholesterol, HDL Cholesterol, Triglyceride, Glucose and HbA1c.

## **8.4. Other Safety Analyses**

The analyses of non-laboratory safety test results including ECGs and vital signs will be based on GSK Core Data Standards, unless otherwise specified. The details of the planned displays are presented in [Appendix 11](#): List of Data Displays.

A listing of changes from baseline in hepatic, prostate (males) and cardiac structure and function assessed via MRI scan will be presented as an exploratory analysis.

Biomarkers will be summarized descriptively. The reproductive tissue biomarkers and bone markers to summarize are given below.

### Reproductive Tissue Biomarkers

Luteinizing hormone, Follicle stimulating hormone, Total testosterone, Free testosterone (calculated) in males and female, Estradiol (females), Dihydrotestosterone, Sex hormone binding globulin and Prostate specific antigen (PSA) (males).

### Bone Biomarkers

Procollagen type I N propeptide (s-PINP) and C-terminal telopeptide of type I collagen (s-CTX).

## **9. PHARMACOKINETIC ANALYSES**

PK concentration related summaries will be presented. No PK parameters will be derived in this RAP. The PK parameters for the Study will be derived as a part of Population Pharmacokinetic (POPPK) analyses. The POPPK RAP will include the detailed population PK analysis and resulting derived PK parameters including Cmax and AUC over dosing interval.

### **9.1. Secondary Pharmacokinetic Analyses**

#### **9.1.1. Summary Measure**

Pharmacokinetic concentration data will be presented in graphical and tabular form and will be summarized descriptively by gender.

#### **9.1.2. Population of Interest**

The secondary pharmacokinetic analyses will be based on the Pharmacokinetic population, unless otherwise specified.

#### **9.1.3. Statistical Analyses / Methods**

Details of the planned displays are provided in [Appendix 11](#): List of Data Displays and will be based on GSK Data Standards and statistical principles.

##### **9.1.3.1. Statistical Methodology Specification**

Plasma concentration time data will be descriptively summarized by the 3 sampling intervals (pre dose, 1-4h interval and 5-8 h intervals) by visit and also listed by treatment group for each gender.

## **10. POPULATION PHARMACOKINETIC (POPPK) ANALYSES**

A population PK analysis will be conducted on the final data. The timeline for these analyses will be independent of the analysis described in this RAP. To support this analysis a NONMEM-specific data file will be generated, the analysis approach and specifications are detailed in the POP PK Data Analysis Plan by CPMS.

To support this analysis two NONMEM-specific data files will be generated by S&P using pre-defined formatted datasets provided by CPMS. The first formatted dataset will focus on the PK data and all relevant covariates. The second dataset will contain the time dependent efficacy and safety endpoints.

## 12. APPENDICES

### 12.1. Appendix 1: Protocol Deviation Management and Definitions for Per Protocol Population

#### 12.1.1. Exclusions from Per Protocol Population

The criteria for subject exclusion from the Per Protocol population are based on 'the Protocol Deviation Specification-version 2.0-31August 2018'. Refer to the latest version of the rules document prior to finalisation of the per protocol population.

The following criteria define the protocol deviations Potential protocol deviations leading to exclusion from PP population will be reviewed by the study team to confirm that they meet these criteria. This review will occur before the clinical database has been frozen for analysis. Note: None of the protocol deviations need the data unblinding to take the decision whether the subject data to be excluded from analysis or not. So, the protocol deviation meeting post unblinding won't be conducted.

A subject meeting any of the following criteria will be excluded from the Per Protocol population:

Number	Exclusion Description
01	Inclusion #1 – Subject not 50-75 years of age inclusive
02	Inclusion #3 – Did not have Confirmed Diagnosis of COPD
03	Inclusion #4 – SPPB: Score of "0" on any component of the SPPB or Timed Chair Stand Score is < 1 and > 3
04	Inclusion #5 – BMI not within 18-32 kg/m  (inclusive)
05	Inclusion #6 – not current smokers or former smokers with a cigarette smoking history of <10 pack years
06	Exclusion #1-7 – Prohibited Medical Conditions
07	Exclusion #8-10 – Prohibited Treatments
08	Exclusion #11 – Prohibited Prior/Current Clinical Study Experience
09	Exclusion #12-13 – Key laboratory tests out of range
10	Exclusion #14 – ECG values above ranges (QTc > 480, QTcB/F > 450)
11	Exclusion #15 – Positive HIV antibody test
12	Any other deviations from inclusion/exclusion criteria which could impact the efficacy assessment.
13	Experience an exacerbation, which needed treatment with steroids during the treatment phase of the study
14	Not completing the Day 80 PROactive endpoint, Week 13 (Day 90) lean mass and all of the functional assessments (leg press strength, peak performance from Incremental shuttle walking test, Constant Work Rate (CWR) duration from endurance shuttle walking test, total SPPB score and handgrip strength).
15	Permanent discontinuation of the treatment during the study treatment period (This check must will be performed by Statistics and Programming).

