6.1. Inclusion Criteria

Participants are eligible to be included in the study only if all of the following criteria apply:

1. Participant must be 50 to 75 years of age inclusive, at the time of signing the informed consent.
2. Male and/or female:

a. Male participants:

A male participant with a partner who is a woman of child bearing potential (WOCPB) must agree to use contraception as detailed in [Appendix 2](#) of this protocol during the treatment period and for at least 5 half-lives of study medication have passed after the last ingested dose [125 days, corresponding to time needed to eliminate study treatment for both genotoxic and teratogenic study treatments *plus* an additional 90 days (a spermatogenesis cycle) for study treatments with genotoxic potential] after the last dose of study treatment and refrain from donating sperm during this period.

b. Female participants:

A female participant is eligible to participate if she is post-menopausal and not a woman of childbearing potential (WOCBP) as defined in [Appendix 2](#). Note: Postmenopausal is defined as 12 months of spontaneous amenorrhea [in questionable

cases a blood sample with simultaneous follicle stimulating hormone (FSH) levels consistent with menopause (refer to laboratory reference ranges for confirmatory levels), or be >60 years of age].

3. Confirmed diagnosis of COPD in accordance with the ATS/ERS criteria [Celli, 2004] with a post-bronchodilator FEV₁/ forced vital capacity (FVC) < 0.70 AND 30% ≤ FEV₁%predicted ≤65% of predicted normal value calculated at Screen using the Quanjer reference equation [Quanjer, 2012].
4. Short Physical Performance Battery (SPPB) with ALL of the following:
 - Timed chair stand score ≥1 AND ≤3
 - No score of “0” on any component of the SPPB (i.e., gait speed, balance, or timed chair stand)
5. Body Mass Index (BMI) within the range 18 - 32kg/ m² (inclusive), where BMI = (weight in kg) / (height in meters)²
6. Current smokers OR former smokers with a cigarette smoking history of ≥10 pack years (1 pack year =20 cigarettes smoked per day for 1 year or equivalent). Former smokers are defined as those who have stopped smoking for at least 6 months prior to Baseline.
7. Participants must be able to read and write in the language used for the provided electronic diary and be able to operate an electronic device to a level that allows them to complete an electronic diary on a daily basis.

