 - ALT $>2\times$ ULN and bilirubin $>1.5\times$ ULN (isolated bilirubin $>1.5\times$ ULN is acceptable if bilirubin is fractionated and direct bilirubin $<35\%$).
 - Haematology – Haemoglobin <10.0 g/dL at screening
 - Prostate Specific Antigen (PSA) >4.0 ng/mL
13. Presence of hepatitis B surface antigen (HBsAg), positive hepatitis C antibody test result at screening or within 3 months prior to first dose of study treatment. NOTE: Participants with positive Hepatitis C antibody due to prior resolved disease can be enrolled, only if a confirmatory negative Hepatitis C RNA PCR test is obtained.
14. QT interval corrected for heart rate by Bazett's formula (QTcB) or QT interval corrected for heart rate by Fridericia's formula (QTcF) >450 msec or QT interval corrected for heart rate (QTc) >480 msec in participants with Bundle Branch Block based on a single ECG.
15. A positive test for HIV antibody.

Other Exclusions

16. More than two moderate/severe COPD exacerbations within the past year
 - Exacerbation is defined as worsening of two or more of the following major symptoms: dyspnoea, sputum volume, sputum purulence OR worsening of any one major symptom together with at least one of the following additional symptoms: sore throat, colds (nasal discharge and/or nasal congestion), fever $> 37.5^{\circ}\text{C}$ without any explained cause, increased cough, increased wheeze.
 - A moderate exacerbation is defined as an exacerbation that requires treatment with antibiotics and/or oral steroids. A severe exacerbation is defined as an event that is additionally associated with hospitalization or emergency room visit.
17. Any moderate/severe COPD exacerbation in the 4 weeks preceding the screening visit.
18. Participants on long term oxygen therapy (LTOT), defined as prescribed continuous oxygen use for >14 hours/day.
19. Clinically diagnosed history of drug or alcohol abuse within 5 years prior to randomization.
20. History of sensitivity to any of the study medications, or components thereof or a history of drug or other allergy that, in the opinion of the investigator or GSK Medical Monitor, contraindicates their participation.
21. Participation in a formal pulmonary rehabilitation exercise program outside or inside the home, either currently or completed within the previous 6 months.

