8.2. Withdrawal from the Study

- A participant may withdraw from the study at any time at his/her own request, or may be withdrawn at any time at the discretion of the investigator for safety, behavioral, compliance or administrative reasons.
- If the participant withdraws consent for disclosure of future information, the sponsor may retain and continue to use any data collected before such a withdrawal of consent.
- If a participant decides to withdraw or is withdrawn by the responsible physician, the reasons for withdrawal and the results of any relevant tests will be recorded in the CRF and the planned follow-up procedures will be performed, where possible.
- If a participant withdraws from the study, he/she may request destruction of any samples taken and not tested, and the investigator must document this in the site study records.
- Refer to the SoA for data to be collected at the time of study discontinuation and follow-up and for any further evaluations that need to be completed. Only the safety assessments scheduled for the follow-up visit should be conducted in these participants as described in the SoA (Section 2).
- **Any participant who experiences a severe COPD exacerbation (i.e., associated with hospitalization or emergency room visit) or an exacerbation that requires treatment with oral steroids will be permanently discontinued from study treatment and should return to the clinic for the follow-up visit within the specified window if possible. Only the safety assessments scheduled for the follow-up visit should be conducted in these participants as described in the SoA (Section 2).**

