10.2. Populations for Analyses

All Participants Population

The 'All Participants Population' is defined as all randomized participants who receive at least one dose of study medication.

Analysis Population

The 'Analysis Population' (AP) is defined as participants in the 'All Participants' population having baseline and at least one post-baseline assessment of the strength, lean mass or functional endpoint.

Per Protocol Population (PP)

The 'Per Protocol Population' will consist of any AP participants who are compliant with protocol-specific criteria and who do not experience an exacerbation during the treatment phase of the study. Participants with specified protocol deviations and those failing to complete the Week 13 functional assessments will be excluded. The Per Protocol population will be used for analysis of strength, lean mass and the functional endpoints.

Pharmacokinetic (PK) Population

The 'PK Population' is defined as participants in the 'All Participants' population for whom a PK sample was obtained and analysed for GSK2881078.

All available data will be used in the analyses as defined in the Populations above. Missing values will not be imputed.

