
 
The 'Analysis Population' (AP) is defined as participants in the 'All Participants' population having baseline and at least one post-baseline assessment of the strength, lean mass or functional endpoint (Section
 
	
 
The 'Analysis Population' (AP) is defined as participants in the 'All Participants' population having baseline and at least one post-baseline
 
	
 
The endpoint PROactive scores also added to the definition.
 

Protocol	Reporting & Analysis Plan	
Statistical Analysis Plan	Statistical Analysis Plan	Rationale for Changes

10.2 in the protocol).
	
assessment of the lean mass or PROactive scores or any of the functional endpoints.
	

 
The 'Per Protocol Population' will consist of any AP participants who are compliant with protocol-specific criteria and who do not experience an exacerbation during the treatment phase of the study. Participants with specified protocol deviations and those failing to complete the Week 13 functional assessments will be excluded (Section 10.2 in the protocol).
 
	
 
The 'Per Protocol Population' will consist of any AP participants who are compliant with protocol-specific criteria and who do not experience an exacerbation during the treatment phase of the study. Participants with specified protocol deviations and those failing to complete the Week 13 functional assessments or PROactive scores or lean mass will be excluded.
 
	
 
The endpoint PROactive scores also added to the definition.
 

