Per Protocol	
 
The 'Per Protocol Population' will consist of any AP participants who are compliant with protocol-specific criteria and who do not experience an exacerbation during the treatment phase of the study. Participants with specified protocol deviations and those failing to complete any of the Week 13 functional assessments or PROactive scores or lean mass will be excluded. This population will be based on the treatment the participant was randomized to. Further details will be given in Section 12.1.1.
 
	
 
Efficacy (Strength, SGRQ, PROactive Constant Work Rate (CWR) duration from endurance shuttle walking test and time for repeated chair rise)
 

Pharmacokinetic (PK)	
 
The 'PK Population' is defined as participants in the 'All Participants' population for whom a PK sample was obtained and analysed for GSK2881078.
 
	
 
PK
 

1. Refer to [Appendix 11](#): List of Data Displays which details the population used for each display.

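### SAP 12.1.1 excludes only steroid-treated exacerbations from the per-protocol set, against the stated definition, and the chair-stand clause in its rule 03 can never be true

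*SAP*

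**What the plan says.** **Definition.** Protocol 10.2 limits the per-protocol set to participants "compliant with protocol-specific criteria and who do not experience an exacerbation during the treatment phase of the study". SAP Section 4 repeats the condition, "who do not experience an exacerbation during the treatment phase of the study", and refers the reader to 12.1.1 for detail. SAP Table 1 has a row for this definition. Both of its columns carry the exacerbation condition without qualifier, and the only reason given for the change is "The endpoint PROactive scores also added to the definition".

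**Exclusion list.** SAP 12.1.1 turns the definition into 15 numbered rules. Rule 13 reads "Experience an exacerbation, which needed treatment with steroids during the treatment phase of the study". Rule 15 reads "Permanent discontinuation of the treatment during the study treatment period". Rule 12 is a catch-all for other eligibility deviations that might affect efficacy assessment. The section says the list is based on version 2.0 of the deviation specification (31 August 2018) and tells the reader to consult the latest version. SAP 4.1 cites version 6.0 (28 November 2019).

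**Chair stand.** Inclusion 4 in Protocol 6.1 requires "Timed chair stand score ≥1 AND ≤3" and no zero on any SPPB component. Rule 03 expresses the breach as a zero on any component, or a chair-stand score `< 1 and > 3`.

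**The concern.** An exclusion list should put the population definition into operation. Here it changes the definition in one place and fails to apply an entry criterion in another.

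On exacerbations, a programmer working from Section 4 and one working from the 15 rules would classify some participants differently, and the SAP does not say which text prevails. The protocol names steroid treatment where it wants that limit, as in 8.2. Section 10.2 contains no such limit. Because Table 1 lists the departures from the protocol and has a row on this very definition, a reader would take it that nothing else had changed.

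On the chair stand, the upper limit of inclusion 4 is part of the functional deficit that defines the target population. A rule that cannot detect a score above that limit leaves the decision to judgement. Fixed wording is preferable, because the study team confirms these exclusions and the trial is sponsor-unblind (Protocol 7.4), although SAP 4.1 does plan blinded data review.

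**Working it through.** The documents give no figure to reproduce on this point. The check runs the rules over the possible cases.

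**1. Exacerbations.** The inputs are:
- Protocol 6.2, no. 16, which defines an exacerbation by symptoms and adds "A moderate exacerbation is defined as an exacerbation that requires treatment with antibiotics and/or oral steroids". An antibiotic-only event, or a milder untreated one, is therefore still an exacerbation.
- The sentence in Protocol 8.2 that begins "Any participant who experiences a severe COPD exacerbation (i.e., associated with hospitalization or emergency room visit". It goes on to add events treated with oral steroids and requires permanent discontinuation of study treatment, which triggers rule 15.

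| Type of exacerbation | Definition (Protocol 10.2, SAP 4) | Rule 13 | Rule 15 via Protocol 8.2 | Excluded by either rule |
|---|---|---|---|---|
| Untreated, non-severe | out | no | no | **no** |
| Antibiotics only, non-severe | out | no | no | **no** |
| Oral steroids, non-severe | out | yes | yes | yes |
| Hospital or emergency room, no steroids | out | no | yes | yes |
| Hospital or emergency room, with steroids | out | yes | yes | yes |

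The definition excludes all 5 types. Rule 13 alone excludes 2, and rules 13 and 15 together exclude 3. The first two rows stay in unless another rule, such as the missing-assessment rule 14, happens to remove the participant. Rule 12 does not close the gap, because it concerns eligibility deviations and not events on treatment.

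**2. Chair stand.** Assumption: each SPPB component scores 0 to 4. This is inferred from the three components in inclusion 4 and the top of the SPPB categories in SAP 12.6.2, with equal maxima: 12 / 3 = 4.

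| Score | Breaches inclusion 4 | `< 1 and > 3` | `< 1 or > 3` | Rule 03 as printed, both halves |
|---|---|---|---|---|
| 0 | yes | false | true | caught, by the zero-score half |
| 1, 2, 3 | no | false | false | not caught, correctly |
| 4 | yes | false | true | **not caught** |

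As printed, the clause is true for 0 of 5 scores. With `or` it is true for 2 of 5, exactly the two that breach inclusion 4. The clause is empty on any scale, since no number is both below 1 and above 3; the 0 to 4 assumption only identifies 4 as the missed value.

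**3. Reach.** Per-protocol efficacy tables in SAP 12.11.5:
- model-based: 2.2, 2.4, 2.13, 2.21, 2.27, 2.32 = 6
- descriptive: 2.7, 2.16, 2.25, 2.30, 2.36 = 5
- total: 6 + 5 = 11, none of them a headline deliverable

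Related displays are Tables 1.6 and 1.7, Listings 8, 9 and 38, and the supportive SAS listings for the per-protocol models. The five Bayesian tables (2.5, 2.14, 2.23, 2.28, 2.34) all use the Analysis Population.

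**The case against.** The best defence is that Section 4 itself sends the reader to 12.1.1, so rule 13 may be read as the announced detail. Alternatively the two texts may be applied together, in which case an antibiotic-only event is already excluded by Section 4. Both readings are possible, but they give opposite answers for the same participant and the SAP does not choose between them. The ambiguity therefore stands.

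The second defence is that the operative rules sit in a later deviation specification that has not been supplied and may already be correct. This is a genuine limit on both parts: one cannot say that the wrong set would be built. It does not repair the SAP, however. If version 6.0 restores the broad rule, the printed rule 13 is out of date. If it keeps the narrow one, Section 4 and Table 1 are wrong.

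The third defence is that rule 03 is shorthand with an evident slip, keyed to an inclusion criterion that the protocol states correctly. That is probably how the error arose, and inclusion/exclusion deviations are listed separately (Listing 7), so a breach would be visible. A reader might infer that a score of 4 can be removed only through rule 12. That goes too far, because Section 4 also requires compliance with the protocol's criteria in general terms.

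A reader might also see a contradiction in SAP 4.1 saying that wrong treatment can be identified only after unblinding, while 12.1.1 says no exclusion decision needs unblinding. The documents do not support making this a defect of the per-protocol set. Section 4 bases that set on randomised treatment, and none of the 15 rules excludes for wrong treatment. Read together, such participants stay and are analysed as randomised.

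**Conclusion.** The point holds, within limits. SAP 12.1.1 as printed does not implement the per-protocol definition: rule 13 is narrower than Protocol 10.2, Table 1 and Section 4, the narrowing is undeclared, and rule 03 contains a clause that can never apply.

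The conflict over exacerbations is confined to non-severe events that were untreated or treated with antibiotics only. It would be wrong to infer that severe exacerbations remain in the set. That conclusion assumes Protocol 8.2 is followed as written; 8.1 words discontinuation after a hospitalised event permissively, and the residual group would widen if 8.2 were not applied. For the chair stand, the only breach that rule 03 misses is a score above 3.

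Nor do the documents support any inference that the trial's main result is at risk. SAP 7.1.3 makes the per-protocol analysis supportive, and the primary and Bayesian results rest on the Analysis Population. The count of 11 tables shows where the rules are used and is not a measure of effect. The documents give no rate of non-steroid exacerbations or of chair-stand breaches, so neither the number of participants affected nor the direction of any bias can be derived.

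**What to change.** Before unblinding:

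1. Reword rule 13 to cover every treatment-phase exacerbation, however treated, to match Section 4 and Protocol 10.2. If the narrowing is intended, declare it with a reason in Table 1 and amend Section 4 to agree.
2. Change the chair-stand clause in rule 03 to `< 1 or > 3`.
3. Check the printed list against the current deviation specification, and cite the same version in SAP 4.1 and 12.1.1.

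The cost is SAP wording and deviation programming. No new data are needed: the exacerbation listing shell (SAFE_L1) already records corticosteroids, antibiotics, hospitalisation and emergency-room visits separately. Broadening rule 13 may reduce the per-protocol set, by a number that the documents do not allow one to estimate.
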